4.1.4. Analysis Visit and Analysis Timepoint

Analysis visit and *analysis time point* are timing variables to be defined in the ADaM specifications document for analyses involving visits. Possible values of these timing variables may vary depending on which assessment is considered.

4.2. Endpoint-Related Definitions

4.2.1. Study Eye and Fellow Eye

The *study eye* of a subject is the eye with worse vision. It will be chosen by the Clinical Investigator at Day 1 (Baseline).

Fellow eye is the non-study eye.

4.2.2. Baseline Score

For any measure, the *baseline score* is the last observed measurement prior to the injection of study medication. For this study, the baseline score would be the measurement prior to the initial injection at baseline visit.

4.2.3. Change from Baseline

For any measure, the change from baseline at a post-baseline visit will be derived as:

Change from Baseline at a Post-Baseline Visit = (Score at the Post-Baseline Visit) – (Baseline Score).

For any measure assessed pre- and post-injection at Baseline, only the pre-injection score will be used to derive the change-from-baseline variable.

4.2.4. Change after Injection

For any measure assessed pre- and post-injection at Baseline, the change after injection will be derived as:

Change after Injection = Post-Injection Score – Pre-Injection Score.

The last pre-injection score and the first post-injection score will be used to derive the change after injection variable.

4.3. Safety-Related Definitions

4.3.1. Adverse Event

As defined in 21 CFR 312.32(a), an AE is any untoward medical occurrence associated with the use of a drug in humans, whether or not considered drug related. AEs reported on the AE electronic Case Report Form (eCRF) will be assessed according to the recently amended FDA regulations 21 CFR Parts 312 and 320.

An AE will be considered as a treatment-emergent AE if the AE onset date is on or after the injection. In other words, an AE will not be counted as a treatment-emergent AE if it can be determined that the AE occurred prior to injection. For AE summaries, only the treatment-emergent AEs will be tabulated.

Each AE will be classified into a system organ classification (SOC) and coded to a preferred term using MedDRA Version 18.0.

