11. ASSESSMENT OF SAFETY

11.1. Adverse Events

11.1.1. Definition of Adverse Events

An AE is any untoward medical occurrence in a subject administered a pharmaceutical product and which does not necessarily have a causal relationship with DE-122. An AE, therefore, can be an unintended sign (including an abnormal laboratory finding), symptom, or disease that has clinical significance and is temporally associated with the use of a medicinal (investigational) product, whether or not related to the medicinal (investigational) product.

In clinical studies, an undesirable medical condition occurring at any time, including baseline or pre-treatment period, may be recorded as an AE even if no DE-122 has been administered.

Any significant adverse change in a subject's condition from baseline, regardless of causality, is to be considered an AE, unless the change is determined to be a continuation of a pre-existing condition that is documented in the subject's medical history. However, a clinically significant worsening in severity, intensity, or frequency of a pre-existing condition may indicate an AE. In addition, all conditions that lead to hospitalizations, defined as an overnight hospital stay, are considered as AEs. This includes planned elective surgeries.

Lack of efficacy of the IVT DE-122 for the condition being investigated is not considered an AE unless a clinically significant change is assessed by the Clinical Investigator. An elective surgical procedure scheduled or planned prior to study entry is not considered an AE if an overnight hospital stay is not required, and the underlying diagnosis for which surgery is to be performed should be captured in the medical history as a pre-existing condition. The surgical procedure should also include the term "elective" in all reports.

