11.1.1.2. Reporting Adverse Events

AEs, whether spontaneously reported by the subject or noted by authorized study personnel, will be recorded in the subject's medical record and on the appropriate AE eCRF. Each recorded AE will be described by its duration (i.e., start and end dates), severity, regulatory seriousness criteria if applicable, suspected relationship to the DE-122, actions taken and outcome.

AEs that occur after any subject has provided written informed consent, before treatment, during treatment, or within 30 days following the cessation of treatment, whether or not they are related to the study, must be recorded. To improve the quality and precision of acquired AE data, Clinical Investigators should observe the following guidelines:

- Whenever possible, use recognized medical terms when recording. Do not use colloquialisms and/or abbreviations.
- If known, record the diagnosis (i.e., disease or syndrome) rather than component signs and symptoms and /or laboratory or test findings (e.g., record congestive heart failure rather than dyspnea, rales, and cyanosis, and enlarged heart on chest x-ray). However, other events that are considered unrelated to an encountered syndrome or disease should be recorded as individual AEs (e.g., if congestive heart failure and severe headache are observed at the same time and are clinically unrelated, each event should be recorded as an individual AE).
- If the diagnosis is not known, then record the leading component sign, symptom or test finding and describe the other clinically related findings in the narrative description of the case. A suspected diagnosis can be used and described as such (e.g., record suspected or probable myocardial infarction); this has to be updated in the clinical database once the diagnosis is confirmed.

AEs occurring secondary to other events (e.g., sequelae) should be identified by the primary cause. A primary AE, if clearly identifiable, generally represents the most accurate clinical term. If a primary AE is recorded, events occurring secondary to the primary event should be described in the narrative description of the case. For example:

The subject developed orthostatic hypotension and subsequently fainted and fell to the floor wherein she experienced a head trauma and neck pain.

The primary AE in this example is orthostatic hypotension. The fall, head trauma and neck pain should be described in the narrative description of the case.

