- For intermittent events (e.g., intermittent headache), the event onset date should be recorded as the date the subject first started to experience the event and resolution date should reflect when the last occurrence resolved or stopped. Separate AEs for each event should not be recorded. For example, if a subject experienced headache on 14SEP2015 lasting for three hours, then subsequently experienced intermittent episodes of headache every day for approximately 3 hours until 21SEP2015, then the AE date of onset is 14SEP2015 and the resolution date is 21SEP2015.
- For intermittent events, record the maximum severity of the individual events. For example, if a subject complains of intermittent headaches for one week and the severity of each headache ranges from mild to moderate, then the severity would be moderate.
- For intermittent hospitalizations occurring for a primary AE (e.g., in a subject with multiple sclerosis, commonly known for its relapsing and remitting course, in some cases leading to multiple hospital confinements), the subsequent hospitalizations should be described in the narrative description of the case.
- If treatment was initiated, include the treatment and duration of the medication(s) in the eCRF.

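### An intermittent adverse event that starts before the DE-122 injection and worsens after it is left out of the SAP's AE tables

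*SAP*

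**What the plan says.** **SAP 4.3.1** sets the rule: "An AE will be considered as a treatment-emergent AE if the AE onset date is on or after the injection". It restates the rule from the other side: "an AE will not be counted as a treatment-emergent AE if it can be determined that the AE occurred prior to injection". It then limits the tables: "For AE summaries, only the treatment-emergent AEs will be tabulated". There is no clause for an event that begins before the injection and gets worse after it.

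**Protocol 11.1.1.2** starts AE recording before dosing. It covers "AEs that occur after any subject has provided written informed consent, before treatment, during treatment, or within 30 days following the cessation of treatment". For intermittent events it fixes three things:
- Onset: "the event onset date should be recorded as the date the subject first started to experience the event".
- Number of records: "Separate AEs for each event should not be recorded".
- Grade: "For intermittent events, record the maximum severity of the individual events".

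**SAP 8.1** plans tables of subjects with AEs by system organ class and preferred term, and again by maximum severity. It separately plans listings of AEs, SAEs, AEs leading to discontinuation, deaths and events of special interest.

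**Protocol 14.7** plans tables of subjects with any AE, without the treatment-emergent limit that the SAP adds.

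**The concern.** Each rule is ordinary on its own. The difficulty comes from combining them. The protocol fixes the onset of an intermittent event at its first episode and rules out a second record. The SAP then uses that onset date as its only test. A subject with a mild episode in screening and a severe one after DE-122 therefore has a single severe record with a pre-injection onset, and the SAP test rejects it.

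Incidence and severity of AEs are among the safety endpoints in Protocol 14.1.1, and safety and tolerability are the primary objective. For the records it affects, the omission can only lower the tabulated post-dose incidence and severity. With 2 or 3 subjects per cohort, one missing record can decide whether a cohort shows an event for a given term at all.

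**Working it through.** The plan states no figure to reproduce, so the check applies the rules to a case.

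**Inputs**
- Test (SAP 4.3.1): treatment-emergent if onset date ≥ injection date.
- Case (Protocol 11.1.1.2, the protocol's own example): intermittent daily headache, one record, onset 14SEP2015, resolution 21SEP2015.
- Screening window (Protocol Table 4): Day -7 to Day -1.
- Study day before injection (SAP 4.1.2): date minus injection date, with no Day 0.
- Cohort sizes (Protocol 14.1.2): 2 or 3 in Cohort 1, then 3 in each of Cohorts 2 to 4.
- Assumption: the example gives no injection date, so it is varied.

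**Step 1. Apply the onset test**

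| Assumed injection date | Study day of 14SEP onset | Onset ≥ injection? | Episodes on or after injection date? |
|---|---|---|---|
| 14SEP | Day 1 | Yes, counted | Yes |
| 15SEP | 14 − 15 = Day -1 | No, excluded | Yes |
| 16SEP to 20SEP | Day -2 to Day -6 | No, excluded | Yes |
| 21SEP | 14 − 21 = Day -7 | No, excluded | Yes (last episode, same date) |

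The seven excluded dates, 15SEP to 21SEP, place the first episode on each day of the screening window in turn. In all seven the record is rejected although episodes continue to or past the injection date.

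**Step 2. Add worsening.** Suppose the episodes before injection are mild and one after it is severe. The maximum-severity rule stores one record: onset 14SEP, grade severe. The onset test does not look at the grade, so the record stays out of the incidence table and the maximum-severity table.

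**Step 3. The exposed window.** This is up to 7 screening days. An event on Day 1 is lost only if it can be shown to have preceded the injection. Otherwise the SAP's wording counts it.

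**Step 4. Size in the tables.** For one affected subject with no other event under that term, a cohort of 3 shows 0 of 3 where 1 of 3 had a post-dose worsening. Across about 12 subjects, the overall row shows 0 of 12 in place of 1 of 12. No event rate is given in the documents, so the chance of this happening cannot be calculated.

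**Step 5. Would a SAP clause alone repair it?** No. The single record holds one onset date and one maximum grade. It does not show whether the severe episode came before or after dosing, so a worsening clause could not be applied to it. The recording rule has to change as well.

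**The case against.** **Other worsening can become a new AE.** The ban on separate records is written for intermittent events only. Protocol 11.1.1 says that "a clinically significant worsening in severity, intensity, or frequency of a pre-existing condition may indicate an AE", and Appendix D (21.4.2) has worsening of earlier findings assessed as an AE. This stands, and it limits the point. A reader might infer that every AE that starts in screening and worsens is lost. The documents do not support that: for non-intermittent AEs they do not say whether worsening opens a new record. Nor does the route clearly rescue the intermittent case. Protocol 11.1.1 says only that worsening may be an AE, and it includes worsening in frequency, which fits poorly with one record per intermittent event. Neither passage assigns a new onset date.

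**The event may still be reported.** The treatment-emergent limit is stated for summaries, and the listings in SAP 8.1 carry no such limit. A reader might infer that the event vanishes from the report; that is not supported. But a listing line with one maximum grade does not show when the worse episode occurred.

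**Other safeguards are unaffected.** BCVA, slit-lamp scores and IOP are compared with baseline whatever the AE onset. Dose escalation rests on the Safety Review Team's review, not on these tables. Both observations stand.

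**The exposure is small.** Screening is short, and Protocol section 5 reports no AEs in the two Cohort 1 subjects who had completed. This also stands. Expressing the loss as a percentage of a cohort would be misplaced, because SAP sections 6 and 7 do not display percentages by dose level.

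**Events after anti-VEGF injections.** A reader might infer that the one-record rule also merges reactions after DE-122 with later ones after anti-VEGF. The protocol's example is daily headache over a week, and nothing makes separate reactions weeks apart one intermittent event. If they were merged with onset after the Day 1 injection, the record would still be treatment-emergent and counted at its maximum severity.

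**Conclusion.** The point holds for a narrow, well-defined case: an intermittent AE whose first episode falls between consent and injection and which worsens after DE-122. Under the rules as written it is absent from the SAP's incidence and maximum-severity tables. For one such event, a cohort count of 1 is shown as 0. The conclusion assumes that sites follow the one-record rule literally and that the subject has no other event under the same term. The frequency is unknown and the window is short, so this is a correctable gap in a definition, not evidence that the safety results would be materially wrong.

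**What to change.** 1. **SAP 4.3.1:** define treatment-emergent as onset on or after the DE-122 injection, or an increase in severity or seriousness after it.
2. **Protocol 11.1.1.2 and the eCRF guide:** state that an AE, including an intermittent one, that began before the DE-122 injection and worsens after it gets a new record. Its onset is the date of worsening, and it carries its own post-injection grade. The severity tables use that grade.

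Both changes are needed, because the SAP clause cannot be applied without the date and grade of the worsening. The second also settles the open question for non-intermittent AEs. The cost is one SAP clause, one recording instruction and a few more AE records.

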4.3.1.1. Severity of Adverse Event

Each AE will be graded by the Clinical Investigator as Mild, Moderate, or Severe based on the criteria specified in Section 11.1.1.1 of the protocol.

4.3.1.2. Serious Adverse Event

An AE will be counted as a serious adverse event (SAE) if the Clinical Investigator answered “Yes” to the AE eCRF question “Is the adverse event serious?”

4.3.1.3. Ocular Adverse Event

An AE will be counted as an ocular AE if the Clinical Investigator selected “OD”, “OS”, or “OU” for “Event Location” on the AE eCRF.

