2. STUDY OBJECTIVE

2.1. Primary Objective and Endpoints

The primary objective is:

- To assess the safety and tolerability of a single intravitreal injection of four dose levels of DE-122 (0.5 mg/eye, 1.0 mg/eye, 2.0 mg/eye and 4.0 mg/eye) in subjects with refractory exudative age related macular degeneration.

The safety and tolerability of DE-122 will be assessed by

- adverse events (AEs)
- indirect ophthalmoscopy
- best-corrected visual acuity (BCVA)
- slit-lamp biomicroscopy
- intraocular pressure (IOP)
- fundus photography
- fluorescein angiography
- serum chemistry
- hematology
- urinalysis
- physical exam
- electrocardiogram (EKG)
- pregnancy test
- vital signs

Section 4.3.2 gives a detailed description of the safety measures to be collected in this study.

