4.3.1.4. Adverse Drug Reaction

An AE will be counted as an ADR if the Clinical Investigator answered “Related” to the AE eCRF question “Relationship to Study Drug?”

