6. GENERAL CONSIDERATIONS

Besides data listings, all measures will be summarized by dose level and/or overall. Continuous variables will be summarized using descriptive statistics such as number of observations (n), mean, standard deviation, minimum, and maximum. Categorical variables will be tabulated using frequency (n), sometimes along with percentage (%). Percentages will not be displayed for summaries by dose level due to the small sample size.

All data manipulations and descriptive summaries will be implemented using SAS[®], Version 9.3 or later.

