7.2. Demographics and Baseline Characteristics

Subject demographics and baseline characteristics will be descriptively summarized for the ITT Population by dose level and overall. Specifically for subject demographics, the following variables will be summarized:

- Age at entry (continuous and categorical: < 65 years or \geq 65 years)
- Sex
- Race
- Ethnicity

For baseline characteristics, the following variables will be summarized for study eyes:

- Baseline BCVA
- Baseline IOP
- Baseline CST
- Baseline macular volume

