8.1. Adverse Event

Subjects with any AE(s) (or ADR(s)) will be tabulated by SOC and preferred term specified in MedDRA Version 18.0. They will also be tabulated by SOC, preferred term, and maximum severity. In these AE tables, a subject who experienced multiple AEs (or ADR(s)) within a SOC or preferred term will be counted only once at the maximum severity for that SOC or preferred term; in addition, ocular AEs (or ADRs) will be presented first to be separated from non-ocular AEs (or ADRs).

AEs, SAEs, AEs leading to discontinuation, and deaths, if any, will be listed separately by dose level, subject ID, and onset time.

ESI(s) will be listed by event type, dose level, and subject ID.

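### The SAP's ocular adverse event tables combine the DE-122 study eye with the fellow eye, so they cannot show which eye an event or its worst grade belongs to

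*SAP*

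**What the plan says.** - **Definition.** SAP 4.3.1.3: "An AE will be counted as an ocular AE if the Clinical Investigator selected" OD, OS or OU as the event location. The eye that received DE-122 plays no part in the definition.
- **Counting.** SAP 8.1 tabulates subjects by SOC and preferred term, and again by maximum severity. A subject with several events "will be counted only once at the maximum severity for that SOC or preferred term". The only anatomical split is ocular before non-ocular.
- **Drug-related subset.** SAP 4.3.1.4: "An AE will be counted as an ADR if the Clinical Investigator answered" that the event was related to study drug. ADRs follow the same layout.
- **Eye terms.** SAP 4.2.1 states that "Fellow eye is the non-study eye", but the AE rules never use the term. The restriction to one eye appears in SAP 7.2: "For baseline characteristics, the following variables will be summarized for study eyes".
- **Level of summary.** SAP 6 says "all measures will be summarized by dose level and/or overall". Protocol 14.1 also has summaries by dose level and overall.
- **Protocol request.** Protocol 14.7 asks for ocular and non-ocular AEs separately, by relationship to treatment and by maximum severity. It asks for no split by eye.
- **Data collected.** Protocol 11.2.13 records event location (OD, OS, OU or not applicable) and relation to injection procedure for each AE.

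**The concern.** AEs come first among the 14 measures introduced in SAP 2.1 by "The safety and tolerability of DE-122 will be assessed by". The treatment is local: a single intravitreal injection in one eye. For such a drug, the ocular AE table will be read for what happened to the injected eye, and the planned table does not isolate that.

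Fellow-eye events are plausible. Protocol 21.4.8 has indirect ophthalmoscopy in each eye at each visit, and protocol 12 has SD-OCT in both eyes at each visit. Protocol 11.2.11 and 11.2.12 add photography and angiography of both eyes at four visits. Protocol 9.2.1 restricts AMD treatment in the study eye only, so the fellow eye may be diseased and treated locally during follow-up.

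With 2 or 3 subjects per cohort, one event in an untreated eye can change how a dose level looks in the table.

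**Working it through.** The plan gives no figure to reproduce. The check applies the written rules to simple cases and then adds an illustration.

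**Step 1: the rules applied to one subject and one preferred term.**

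| Events | Study eye alone | Table under SAP 4.3.1.3 and 8.1 |
|---|---|---|
| Fellow eye only, mild | not counted | counted, mild |
| Study eye mild, fellow eye severe | counted, mild | counted, severe |
| Study eye severe, fellow eye mild | counted, severe | counted, severe |
| Study eye only, mild | counted, mild | counted, mild |

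Read as a statement about the treated eye, the pooled table can raise the count or the worst grade but never lower either. In a cohort of 3, the first row moves the count from 0 of 3 to 1 of 3.

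**Step 2: which tables are affected.** The first two rows always apply to the all-cause ocular table. They reach the ADR table only if the investigator calls the fellow-eye event related to DE-122.

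**Step 3: who is still at risk.** Protocol 5 reports that 2 Cohort 1 subjects completed with no AEs. Cohorts 2, 3 and 4 remain, with 3 subjects each. A third Cohort 1 subject, replacements and added subjects are left out.

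**Step 4: illustration.** Assume a chance p of any ocular AE per eye over follow-up, equal in both eyes and independent between eyes and between subjects. The range 5-20% is an assumption; the documents give no rate.

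- Chance that a cohort of 3 has at least one event in a given set of eyes: a = 1 - (1 - p)^3.
- Chance that its ocular count is non-zero because of fellow eyes only: a × (1 - a).
- Expected number among three cohorts: 3 × a × (1 - a).

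| p | a (study eyes only) | a × (1 - a) | Pooled chance of a non-zero count | Expected cohorts of 3 |
|---|---|---|---|---|
| 0.05 | 0.143 | 0.143 × 0.857 = 0.122 | 0.265 | 0.37 |
| 0.10 | 0.271 | 0.271 × 0.729 = 0.198 | 0.469 | 0.59 |
| 0.20 | 0.488 | 0.488 × 0.512 = 0.250 | 0.738 | 0.75 |

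The pooled chance is 1 - (1 - p)^6 and equals the sum of the two columns before it. For example, 0.271 + 0.198 = 0.469.

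No probability is offered for the severity case in the second row of Step 1. It needs the same term in both eyes of one subject at different grades, and the documents give nothing to estimate that from.

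**The case against.** The strongest reply is that the table is correctly labelled. It counts subjects with ocular AEs, not events in the treated eye, and it does what protocol 14.7 requests. An inventory covering both eyes also has a safety purpose: protocol 11.1.3 makes any ocular telangiectasia or bleeding an event of special interest without limiting it to the study eye. Over-counting is the cautious direction for safety. With about 12 subjects and no hypothesis, readers can go to the listings. All of this stands, and it is why the point is an improvement and not a defect against the protocol. What remains is that SAP 8.1 gives the listings' sort order but not their columns, and that a listing does not change a summary table read alone.

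A reader might also infer that a table of relation to injection procedure is missing. The field is collected (protocol 11.1.1.1 and 11.2.13) and no SAP summary uses it. But protocol 14.7 does not ask for such a table, and events attributed only to the procedure already fall outside the ADR table. The documents also do not say whether the field separates DE-122 injections from anti-VEGF injections. A listing column is enough.

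An eye split has a limit of its own. Severity is graded per event (SAP 4.3.1.1), so the grade of an OU event may reflect the fellow eye.

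**Conclusion.** The point holds as a worthwhile, inexpensive improvement. Under the written rules the ocular AE summary cannot show whether an event or its worst grade belongs to the eye that received DE-122, and one fellow-eye event can turn 0 of 3 into 1 of 3. That follows from the text and needs no assumption. The 0.37 to 0.75 cohorts is illustrative only. It rests on the assumed 5-20% rate, equal and independent in both eyes, and on three cohorts of 3.

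Three stronger readings are not supported:

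- **That the pooled count is an error or contradicts the protocol.** It is a valid subject-level count of the kind protocol 14.7 describes.
- **That dose escalation is affected.** Under protocol 7.4 those decisions rest on the Safety Review Team's review of safety parameters. These tables do not drive them, and SAP 6.5 plans no formal interim analysis.
- **That 3 × 0.143 = 0.43 to 3 × 0.488 = 1.46 cohorts would show a count caused by fellow eyes alone.** Those figures count cohorts with any fellow-eye event. They describe fellow eyes as the sole cause only if study eyes have no events at all.

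**What to change.** In SAP 4.3.1.3, classify each ocular AE as study eye or fellow eye by comparing its location with the subject's designated study eye. Place OU events in the study-eye category.

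In SAP 8.1, tabulate ocular AEs and ocular ADRs separately for the two categories, taking maximum severity within each. Add a footnote that severity is graded per event, so the grade of an OU event may not be specific to the study eye. Fellow-eye events stay visible in their own category.

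Name eye (study or fellow) and relation to injection procedure as columns in the AE and ESI listings. No separate table of procedure relation is needed.

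**Cost.** SAP wording, a derived variable and a few more sparse tables, with cells of 0 to 3 subjects per dose level at the planned cohort sizes. The sparse tables are the main drawback. Both fields are already collected, so data collection, sample size and clinical management do not change.
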